## ABSTRACT

A large percentage of women suffer low back and pelvic pain both during and after pregnancy. There are several factors to which these complaints are attributed, even affecting their daily lives. It is identified that many of these women do not receive adequate health care, however, different physiotherapeutic interventions are recommended to alleviate these conditions, presenting moderate levels of evidence. Virtual reality is presented as a complementary and promising treatment method to physiotherapy for the improvement of fundamental variables such as perceived pain and pain avoidance. The main objective is to evaluate the efficacy of a combined VR and physiotherapy program of 4 weeks duration compared to a standard physiotherapy intervention in pregnant women with low back pain and pelvic pain for the improvement of pain avoidance, pain intensity, disability and functional level. As a secondary objective we propose to investigate patient satisfaction with the VR intervention. This research will be carried out by means of a multicenter randomized controlled clinical trial in pregnant patients residing in the provinces of Seville and Malaga with a diagnosis of low back pain and pelvic pain during pregnancy. The alternative hypothesis of this research is that the implementation of a Virtual Reality program together with standard physiotherapy in pregnant patients with low back and pelvic pain presents better clinical results obtained with the current standard intervention, which may represent an opportunity to define new policies and interventions for these pathologies and their consequences.

## KEYWORDS

Virtual Reality, Physiotherapy, Low-back pain, Pelvic pain, Pregnancy

## Background

Approximately 50% of women experience low back pain (LBP) during pregnancy; 25% continue to experience pain 1 year after delivery (1). Low-back pain (LBP) and pelvic pain (PP) are common during pregnancy and tend to increase as pregnancy advances; in some cases, the pain radiates into the buttock, leg and foot (2). Global prevalence is reported to range from 24% to 90%, in part, because there is currently no universally recognised classification system for the condition (3). For many women, pain can become so severe that it interferes with ordinary daily activities, disturbs sleep with repercussions in social and sexual life, work capacity and increased psychological stress and contributes to high levels of sick leave (4). Several factors have been identified as the possible causes of back pain in pregnancy. Mechanical strain secondary to enlarge gravid uterus is one of the causative factors which leads to compensatory lumbar lordosis (5). Besides that, separation of the abdominal muscles during pregnancy does contribute to paraspinal muscle strain. Relaxin hormone which is elevated during pregnancy is also identified as a causative factor. Hence, there will be an increase in joint laxity which may caused instability rotatory movements of sacroiliac joints (6,7).

It is estimated that over 50% of women receive little or no intervention from healthcare providers (8). European guidelines recommend that LBP and PP, are managed by providing adequate information and reassurance to patients that it is best to stay active, continue normal daily activities and work if possible, and by offering individualised exercises where appropriate. Similarly, prenatal practitioners in the United Kingdom and Nordic countries give women information about how to manage LBP, PP or both during their pregnancy and may refer them to physiotherapy for a more specific treatment programme. However, in the United States, women are taught that LBP is a normal part of pregnancy. Interventions that have been used to date to help manage the pain include exercises, frequent rest, hot and cold compresses, abdominal or pelvic support belts, massage, acupuncture, chiropractic, aromatherapy, relaxation, herbs, yoga, Reiki, paracetamol, and nonsteroidal anti-inflammatory drugs (3,4,8,9). Other forms of therapy have been studied including exercise, yoga, progressive muscle relaxation, manual therapy, acupuncture, alone or with exercises, multi-modal

approach, including manual therapy, exercise and education, pelvic belts, kinesio tape and transcutaneous electrical nerve stimulation (TENS). A Cochrane systematic review and metanalisis from 2015 conclude that there is low-quality evidence that exercise may reduce pregnancy-related low-back pain and moderate to low-quality evidence suggesting that any exercise improves functional disability and reduces sick leave more than usual prenatal care (2). Another Systematic review from 2018 including 32 studies conclude that compared with not exercising, prenatal exercise decreased the severity of LBP, PP, during and following pregnancy (1).

Some studies addressed the issue of sick leave during pregnancy, presenting positive results through exercise programs, reducing healthcare costs and promoting women's health (10,11). Recommended physical treatments, particularly for persistent low back pain (>12 weeks duration), include a graded activity or exercise programme that targets improvements in function and prevention of worsening disability. Since evidence showing that one form of exercise is better than another is not available, guidelines recommend exercise programmes that take individual needs, preferences, and capabilities into account in deciding about the type of exercise. Some guidelines do not recommend passive therapies, such as spinal manipulation or mobilisation, massage, and acupuncture, some consider them optional, and others suggest a short course for patients who do not respond to other treatment (12). Other passive electrical or physical modalities, such as ultrasound, transcutaneous electrical nerve stimulation progressive relaxation, and mindfulness-based stress reduction and combined packages of physical and psychological treatment, for those with persistent LBP who have not responded to previous treatments (13–15). For patients who have not responded to firstline treatments, and who are substantially functionally disabled by pain, multidisciplinary rehabilitation programmes with coordinated delivery of supervised exercise therapy, cognitive behavioural therapy, and medication are more effective than standard treatments (13–18).

A clinical practice guidelines in LBP during pregnancy in Spain suggests the use of aquatic exercises and other individualized exercise programs, as well as therapeutic massage to relieve low back pain during pregnancy (19). Furthermore,

physiotherapy was effective in relieving back pain by increasing the strength of the lumbo-sacral joint and pelvic girdle muscles (20). By introducing exercise as one of the treatments for back pain in pregnancy, it is hope to reduce the pain suffered by these women and hence reduce the morbidities associated with it. It is also aims to improve the quality of life (6).

Virtual Reality: Virtual reality (VR) is a new technology, which has been rapidly evolving over the past 2 decades (21). VR can be operationally defined as “simulations that make use of various combinations of interaction devices and sensory display systems” (22,23). VR has been explored in a variety of fields and clinical applications. In healthcare, VR technology can be used to provide treatment (24), facilitate pain management (25) and rehabilitation (12) among others.

A systematic review from 2019 conclude that VR has the potential to improve outcomes for spinal pain with demonstrated statistical and clinical significance (26). Additional patient populations with benefit from VR interventions include individuals with higher pain and physical dysfunction levels, anxiety, an alternative treatment to opioid analgesics (26). A randomized control trial in 80 female patients with breast cancer at a specialized cancer center in Jordan shown that immersive VR is an effective distraction intervention for managing pain and anxiety. Using immersive VR as an adjuvant intervention is more effective than morphine alone in relieving pain and anxiety (27). In stroke patients VR show promise as a future tool in the rehabilitation of daily live activities, particularly in the subacute phase (27). VR allows the user to experience the interaction with a computer-generated environment and the simulation of realistic environments and real-life exercises (26). In the rehabilitative context, motivation is an important factor influencing the performance outcome (26). VR constitutes an enriched environment with augmented multiple sensory feedbacks (auditory, visual, tactile), with moving avatars, engaging several neuronal circuits that potentiate patient's learning and recovery (28–30). Thus, VR may be considered a good candidate to help patients in improving their own movements, body position perception and reducing pain during the VR exercises (31). A systematic review from 2019 focus on orthopedic rehabilitation conclude that the evidence of VR effectiveness is promising in chronic neck pain and shoulder impingement syndrome. VR and exercises have

similar effects in rheumatoid arthritis, knee arthritis, ankle instability, and post-anterior cruciate reconstruction. For fibromyalgia and knee arthroplasty, the evidence of VR effectiveness compared to exercise is absent or inconclusive (32). A recent Systematic review from 2020 suggest that VR exercise has the potential to exert a positive impact on individual's physiological, psychological, and rehabilitative outcomes compared with traditional exercise (33). VR can also be used for various purposes in different stages of pregnancy: reducing their anxiety levels and training them to effectively manage their pain during labor (34), reducing anxiety before cesarean, episiotomy repair, dilation and curettage (35–38), reducing pain (29), and managing exercise training (24).

Despite the fact that VR has been shown to be effective in some orthopedic conditions, there is no evidence about the effectiveness of VR interventions in LBP and PP during pregnancy. Considering the current health, it is advisable to carry out VR effectiveness studies in this group population both in the hospital environment and in other areas of care.

## Objectives

The main objective of this research is to evaluate the effectiveness of a combined VR and Physiotherapy 4-weeks program compared to a standard physiotherapy intervention in LBP and PP pregnancy woman's to improve pain-related fear avoidance, pain intensity, disability and functional level.

The secondary aim is to investigate patient satisfaction with the VR intervention.

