### Recruitment

In order to generate sufficient data for the development of this research a sample size of (n= 66) patients will be recruited based on previous and concluded RCT for the treatment of LBP or PP (41–43). It was calculated that a sample size of 33 women per cohort could detect a difference in outcomes of 1.0 between the VR intervention and control groups, given a SD of 1.5 and a power of 0.80.

The strategies to achieve an adequate inclusion of participants that reach the target sample size include the multidisciplinary collaboration of the gynecology, rehabilitation and physiotherapy department. The collaborators have been informed about the characteristics of the study in personal interviews and presentation. Recruitment of patients must have a socio-demographic diversity in relation to their social origin, gender, ethnicity and education adapted to the particularities of the reference population.

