## [Outcomes and Instruments](#)

### [Primary research outcomes](#)

- Pain-related fear avoidance (FACS): The Fear-Avoidance Components Scale (FACS) was developed, which incorporates important components of previous FA-related measures, and includes components of the FA model not previously considered in the earlier-developed questionnaires, within a framework of the most current FA model of Vlaeyen (44,45). The FACS has demonstrated acceptable test/retest reliability ( $r = .90\text{--}.94$ ) and internal consistency (Cronbach  $\alpha=.92$ ) (46).

Pain-related fear avoidance (FA), a common problem for patients with painful medical conditions, involves pain-related catastrophizing cognitions, hypervigilance, and avoidance behaviors, which can ultimately lead to decreased functioning, depression, and disability (47).

- Pain intensity: (Visual Analogue Scale VAS): The VAS has been used in previous studies investigating changes in pain and, specifically, in all the randomized trials of interventions for back pain in pregnancy included in or published since the Cochrane and systematic reviews (42). The visual analog scale (VAS) was used for assessment of pain before and after the intervention. Measurement will be performed with a 10-cm scale marked with 1-cm increments. Pain felt by participants will be recorded. Pain was rated on a scale of 0 a 10, with 10

representing the most excruciating pain. The value indicated on the scale by the participants was used as the score. Previous studies have shown that the reliability of the VAS ( $r=0.76-0.84$ ) is high (46).

- Disability and Physical function: In this paper, we focus on the 2 back-specific measures of function recommended in the “core-set,” the Roland-Morris disability Questionnaire (RMDQ) and the Oswestry Disability Index (ODI). They are the most commonly used measures of function in back pain research (46).

The RMDQ will be used for measurement of the severity of disability in participants who had less severe LBP. There are 24 categories comprised of yes or no questions. Each participant can have a maximum score of 24. Scoring closer to 24 indicates greater functional disability (48,49). Quoted test-retest correlations include 0.91 (same day), 0.88 (1 week), and 0.83 (3 weeks) (48).

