The Oswestry low-back pain disability index (ODI) will be completed by the participants and included 10 questions assessing activities of daily living in order to examine the functional level when experiencing LBP. Each category will be scored from zero to five with regard to the severity of disability caused during daily life. The intraclass correlation coefficient was  $r=0.938$ , and the Cronbach’s alpha was 0.918 (day 1) and 0.895 (day 7) in the validation (44,45).

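### Four unranked primary scales have no rule for success, and the sample size does not say which scale its difference of 1.0 and SD of 1.5 refer to

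*Protocol*

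**What the plan says.** The Objectives section gives one main aim with four targets: "to improve pain-related fear avoidance, pain intensity, disability and functional level". Under "Primary research outcomes" the protocol assigns an instrument to each: FACS for fear avoidance, VAS for pain, RMDQ for disability and ODI for functional level. The data collection section lists the same four at baseline (T0) and at four weeks (T1). None is placed above another.

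The Statistical analysis section sets one significance threshold, p < 0.05. It does not say what pattern of results across the four scales would count as success.

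The Recruitment section plans 66 women, 33 per arm, "based on previous and concluded RCT for the treatment of LBP or PP" (references 41–43). It says this could detect a "difference in outcomes of 1.0 between the VR intervention and control groups, given a SD of 1.5 and a power of 0.80". It does not state the scale, the sidedness of the test, any baseline adjustment or any dropout allowance.

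**The concern.** A reader cannot tell which result would make the trial positive. A significant FACS with a null VAS, or the reverse, has no agreed meaning and could be presented either way. The two natural rules have opposite consequences. If any one scale is enough, the chance of a false claim exceeds 5% unless a correction applies. If all are needed, that chance is controlled but power is limited by the weakest scale.

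The sample size does not settle the matter. One difference and one SD in raw points cannot describe four scales with different units, and until the scale is named nobody can judge whether 1.0 is a sensible target. The stated power also does not follow from the stated inputs under a plain t-test.

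**Working it through.** **Inputs.** Difference 1.0, SD 1.5, power 0.80 and 33 per arm come from Recruitment. Alpha 0.05 comes from Statistical analysis. Sidedness is not given, so both versions are shown. Correlations between scales are not given, so those below are assumptions.

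**1. The protocol's own sample size.** Standardised difference d = 1.0/1.5 = 0.667.
- Normal formula, n per arm = 2(z_alpha + z_power)² × SD²/difference². Two-sided: 2 × (1.960 + 0.842)² × 2.25 = 35.3, so 36. One-sided: 2 × (1.645 + 0.842)² × 2.25 = 27.8, so 28.
- The t-test (noncentral t) requires 37 and 29 per arm respectively.
- The stated 33 matches neither. Power of the t-test at 33 per arm is 76% two-sided and 85% one-sided.
- Two-sided, 33 per arm reaches 80% at a difference of 0.70 SD, which is 0.70 × 1.5 = 1.05 points.

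**2. Which scale?** One raw point means different things on different instruments:
- VAS, 0 to 10: 1/10 = 10% of the range.
- RMDQ ("Each participant can have a maximum score of 24"): 1/24 = 4.2%.
- ODI, ten items ("Each category will be scored from zero to five"): 1/50 = 2% if the items are summed. The protocol does not state the total.
- FACS: no range is given.

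The pointers favour VAS. Reference 42 is among the sources for the sample size and is also cited for VAS having been used "in all the randomized trials of interventions for back pain in pregnancy". VAS above 4/10 is an entry criterion. None of this amounts to naming the scale.

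**3. If any one of four scales sufficed, each at two-sided 0.05 with no correction.**
- Independent scales: 1 − 0.95⁴ = 18.5%.
- Equal correlation 0.5, 0.8 and 0.9 (simulated four-variate normal, 2,000,000 draws): about 16%, 11% and 9%.

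**4. If all four were required.** Each test stays at 0.05, so type I error is not inflated. Joint power is at most the lowest single-scale power. No figure is given because the protocol states no effect or SD by scale.

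**5. Holm across four scales.** The strictest step uses 0.05/4 = 0.0125. For an effect of 0.667 SD on one scale, with 33 per arm, the two-sided t-test at that level has 56% power. This is a floor: power is higher when other scales are also rejected, because the later steps are less strict.

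**The case against.** **A statistical analysis plan may exist.** It could hold the multiplicity method, so the absence of a correction in the protocol is not itself the finding. Which outcome decides the trial, and which scale the stated sample size uses, are protocol matters.

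**The Results section calls this a pilot.** The Discussion leaves large trials to future work, and the analysis section promises effect sizes and precision. That softens the point. It does not remove it, because the Abstract and Objectives state an efficacy or effectiveness aim and Recruitment gives a powered sample size.

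**Stronger readings that the protocol does not support:**
- A reader might infer from Table 2, where RMDQ and ODI share a row, that even the number of primary outcomes is unclear. It is not. The objective, the instrument descriptions and the assessment schedule all give four targets with one instrument each; the shared row is layout.
- A reader might infer that the trial has an 18.5% false-positive rate. Nothing says one significant scale suffices, and independence is implausible for two back-disability questionnaires.
- A reader might infer that 33 per arm is an arithmetic error. That is not shown. If 1.5 is the SD of final scores and the analysis adjusts for baseline, dividing the SD by allowing for a correlation of about 0.3 (SD × √(1 − 0.3²)) brings power at 33 per arm to about 80%. A one-sided test with an assumed 10% dropout also leads there: 29/0.90 = 32.2, so 33. The protocol states neither route.
- A reader might take 56% as the power under Holm. It is the worst case for one scale, and it borrows the 0.667 SD effect for whichever scale is tested.

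**Conclusion.** The point stands in two parts. First, four primary scales share one threshold with no ranking and no rule for success. Second, the sample size names no scale, and its stated 80% power is not reproduced by an unadjusted t-test at 33 per arm.

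The 76% rests on a two-sided 0.05 unadjusted test, SD 1.5 and 33 analysed women per arm. The range from 18.5% down to about 9% applies only if any one scale suffices uncorrected, with the assumed correlations. It also takes RMDQ from every participant, as the assessment schedule implies. The instrument description instead speaks of "participants who had less severe LBP", which is a separate matter to reconcile.

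VAS as the source of 1.0 and 1.5 is a reasonable inference and no more than that.

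**What to change.** Amend the protocol, with a date, before outcomes are compared by arm.

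**Success rule, one of two:**
1. Name one primary scale at T1, compared between arms, and make the other three secondary. The choice is the sponsor's.
2. Keep all four as primary and judge each on its Holm-adjusted p-value.

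**Sample size statement:** name the scale, state that the test is two-sided, and do one of the following:
- restate the power as 76% for a difference of 1.0 (80% for 1.05, i.e. 0.70 SD) with 33 per arm, SD 1.5 and an unadjusted t-test; or
- state the baseline adjustment and the assumed baseline correlation that give 80%.

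**Timing:** the protocol places enrolment, data collection and first results in late 2022. If arms have already been compared, report all four scales with Holm adjustment and say that the rule was set afterwards.

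**Cost:** no extra patients or visits. Under an unadjusted test the stated power is slightly lower. With one primary, the other scales cannot carry a positive conclusion alone. With Holm, power for a single scale may be as low as 56% for an effect of 0.667 SD.

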## Methods

### Study design and setting

This research is a 4-week prospective multicentre randomized clinical trial. Participant recruitment and the supervised VR program component will be provided by clinical setting at department of Physiotherapy at University of Sevilla and Málaga (Spain). This research involves departments of gynecology rehabilitation, physiotherapy and researches from the University of Granada,

University of Málaga and University of Sevilla. This research follow the guidelines on Standards for Quality Improvement and Excellence in Reporting (SQUIRE) (39) and is carried out in accordance with CONSORT (Consolidated Standards of Reporting Trials) criteria (40).

The study was approved by the institutional ethics committee of Andalucía with internal code 1928-N-21. All female participants must provide informed consent prior to enrollment in the study.

#### [Participants and eligibility criteria](#)

The trial includes pregnant women suffering from LBP, PP or the two in combination as reported symptomatically by the women or diagnosed by clinicians.

Patients must live in Sevilla or Málaga during the intervention phase, patients with history of LBP or lumbar pathology before pregnancy or have suffered LBP or PP events prior to the first contact with this research. Patients will be excluded if they have any absolute or relative contraindications such as heart disease, chronic obstructive lung disease, diabetes mellitus, incompetent cervix/cerclage, multiple gestation, risk of premature labor, preeclampsia/pregnancy-induced hypertension, thrombophlebitis, pulmonary embolism, intrauterine growth restriction, or serious blood disease, history of abortion or curettage. Also, patients are not in full cognitive capacity that allows them to use new technology tools will be excluded. Inclusion and exclusion criteria is show in Table 1.

Inclusion criteria	Exclusion criteria
Adult woman over 18 years old	Patients with LBP or PP pain prior to pregnancy.
Pregnant woman with Low Back Pain, Pelvic Pain or both conditions with symptomatic character.	Cognitive ability not suitable for the use of technological tools.
Pregnant woman between the 12th and 36th week of gestation, corresponding to the 2nd and 3rd trimester.	Patients with absolute or relative contraindications.
Pain intensity greater than 4/10 on VAS, indicating moderate-severe pain.	
Live in Sevilla or Málaga during the research period.	

Table 1. Inclusion and Exclusion criteria

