### Intervention

Participants will be assigned randomly to the intervention or control groups using a random number table. Both groups will receive 3 sessions per week during the 4 weeks of intervention.

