#### Data collection, monitoring, and management

Once participants have been informed and agree to participate in the study, data will be collected for statistical analysis. This data collection will take place in the period September-December 2022. Initial assessment (Pre) and final 4-week assessment (Post) will be carried out by the research team including, rehabilitation and physiotherapy department. The data will be aggregated to research database created for this purpose and managed by the principal's researches using exportable data tables for statistical analysis.

The research is designed in 4 stages as presented at Figure 1 study design flow diagram:

Stage 1 includes 2 different processes: firstly the identification of candidates, the provision of prior information and the signing of informed consent if subjects agree to participate. Secondly, the assessments by the physiotherapy department. The initial assessment includes a self-made clinical interview for anamnesis with self-administered questionnaires, which will be completed including FACS, RMDQ, ODI and VAS (T0-Pre). This stage ends with the referral to the physiotherapy intervention team.

Stage 2 includes: Design of a personalised physiotherapy programme (CG and EG) according with Physiotherapy department plus VRi intervention in the (EG).

Stage 3 includes: 4 weeks physiotherapy intervention plus VRi program with the supervision of the physiotherapy department. Initials 1 to 1 session is offered with technology management and patient education. Daily follow up sessions include the progression and adverse events records. Physiotherapy team will update programmes according to participant's feedback.

Stage 4 includes: Final assessments and evaluation (T1-Post). At this stage Physiotherapy team and principals researches compile the results of outcomes after 4 weeks including FACS, RMDQ, ODI, VAS and USEQ. Satisfaction questionnaire will be added to research data's for statistical analysis.

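### Entry is open to the 36th week with the only follow-up 4 weeks later, so some of the latest entrants will have delivered before their outcome is measured

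*Protocol*

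**What the plan says.** The inclusion column of Table 1 (Protocol, Participants and eligibility criteria) lists: "Pregnant woman between the 12th and 36th week of gestation, corresponding to the 2nd and 3rd trimester". Under Intervention, "Both groups will receive 3 sessions per week during the 4 weeks of intervention", which is 12 sessions per woman.

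The section on data collection, monitoring and management sets two assessments only: "Initial assessment (Pre) and final 4-week assessment (Post) will be carried out by the research team". Stage 4 of the same section says that the team will "compile the results of outcomes after 4 weeks including FACS, RMDQ, ODI, VAS and USEQ", so all four primary instruments are read once after baseline, at T1.

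The Objectives section states the question as a comparison of the combined programme "compared to a standard physiotherapy intervention in LBP and PP pregnancy woman's to improve pain-related fear avoidance, pain intensity, disability and functional level". The exclusions closest to the timing of delivery are "multiple gestation, risk of premature labor, preeclampsia/pregnancy-induced hypertension". These concern early or complicated delivery, not ordinary delivery at term. The protocol does not require a woman to be still pregnant at T1, does not bring T1 forward, and does not say what is recorded if she delivers during the 4 weeks.

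**The concern.** Two rules that the protocol itself fixes do not fit together at the end of the entry window. A woman entered at the upper limit reaches T1 around her due date. If she has delivered by then, the programme will probably have been cut short, and she has no intermediate assessment to fall back on. Her T1 is either absent or describes a woman who is no longer pregnant. Followed exactly as written, the protocol therefore produces, for some women, an outcome that does not answer the stated question.

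The affected women are not a random part of the sample. The Background says that these pains "tend to increase as pregnancy advances", and entry requires pain above 4/10, so late-gestation women may be well represented; the protocol does not say how entry will be spread. The planned 66 also carries no stated allowance for lost outcomes. A statistical analysis plan can say how to analyse missing or post-partum values, but it cannot move the entry window or the assessment date.

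**Working it through.** **Inputs from the protocol.** Entry from the 12th to the 36th week; programme and T1 at 4 weeks; 66 women, 33 per arm; difference 1.0, SD 1.5, power 0.80; significance at 0.05, with sidedness not stated.

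**Timing, from the protocol alone.** 36 + 4 = week 40. If the 36th week is counted ordinally (35 weeks 0 days to 35 weeks 6 days), T1 falls between 39 weeks 0 days and 39 weeks 6 days. Either reading puts T1 at about week 39 to 40.

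**Chance of delivery before T1.** The protocol gives no delivery distribution, so this part rests on an assumption: gestational age at delivery is Normal with mean 39.0 to 39.5 weeks and SD 1.5 to 2.0. For a woman still pregnant at entry week *e*,

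P = [F(*e*+4) − F(*e*)] / [1 − F(*e*)].

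Example with *e* = 36, mean 39.0, SD 1.5: F(40) = Φ(0.667) = 0.7475 and F(36) = Φ(−2.0) = 0.0228, so P = (0.7475 − 0.0228) / (1 − 0.0228) = 0.742.

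All four corners of the assumption:

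| Entry week | 39.0 / 1.5 | 39.0 / 2.0 | 39.5 / 1.5 | 39.5 / 2.0 | Range |
|---|---|---|---|---|---|
| 36 | 74% | 67% | 63% | 58% | 58-74% |
| 35 | 50% | 49% | 37% | 39% | 37-50% |
| 34 | 25% | 30% | 16% | 22% | 16-30% |
| 33 | 9% | 16% | 5% | 11% | 5-16% |
| 32 | 2% | 7% | 1% | 4% | 1-7% |

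**Whole trial.** Averaging P over entry weeks:

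- Even entry over weeks 28-36: 11-17%. 66 × 0.110 = 7.3 and 66 × 0.171 = 11.3, so about 7 to 11 women.
- Even entry over weeks 12-36: almost all the risk lies after week 28, so this is close to 8/24 of the figure above, 3.7-5.7%. 66 × 0.037 = 2.4 and 66 × 0.057 = 3.8, so about 2 to 4 women.

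**Sensitivity to the assumption.** Widening the mean to 39-40 weeks and the SD to 1.3-2.0 gives 49-78% at week 36, 6-30% at week 34, 2-6% overall with even entry over weeks 12-36 (1 to 4 women), and 6.5-17% over weeks 28-36 (4 to 11 women).

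**Effect on power if T1 is lost.** The plan has no figure for delivery or loss; its only related figure is 33 per arm. The usual formula gives n = 2 × (1.960 + 0.842)² × 1.5² / 1.0² = 35.3, so 36 per arm two-sided (28 one-sided); neither reproduces 33. Two-sided power at 33 per arm is Φ(1.0 / (1.5 × √(2/33)) − 1.960) = Φ(2.708 − 1.960) = 0.773. With 5%, 10% and 15% of T1 values lost it becomes 0.752, 0.729 and 0.704. The 33 is a separate sample-size matter; it matters here only because it leaves no slack.

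**The case against.** The strongest reply is that the problem is confined to the edge of the window. Weeks 34 to 36 are 2 of 24 weeks, about 8% of it; the risk is small by week 32; and with even entry only a handful of women are touched. Power then falls by about two percentage points (0.773 to 0.752 at 5% loss). This stands, and it limits the weight of the point. The exclusions for risk of premature labor, multiple gestation and related conditions also make the wider spreads of delivery time less plausible, though they do not touch delivery at term.

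Three stronger readings are tempting and are not supported.

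- A reader might infer a bias between arms. Gestational week is fixed before randomisation and both arms have the same schedule, so nothing in the protocol makes delivery before T1 favour one arm.
- A reader might infer that the instruments become invalid after delivery. The protocol describes them as a generic pain scale, a fear-avoidance scale for painful conditions and two back-specific function measures; none is presented as specific to pregnancy. Because they are self-reported, delivery need not make T1 missing either. What changes is the state being measured.
- A reader might infer that delivery simply removes the cause of the pain. The Background names mechanical strain as one cause among several and reports that 25% of women still have pain a year after delivery. The direction in which post-partum values would move the estimate is therefore not established.

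It could also be said that missing data and covariates belong in an analysis plan that is not shown. That is fair for how the values are analysed. It does not answer the mismatch between entry window and assessment date, which the protocol sets.

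**Conclusion.** The point holds, in a limited form. The upper entry limit and the fixed 4-week T1 are inconsistent with measuring every woman during pregnancy, and this follows from the protocol's own dates. How often it happens rests on the assumed delivery distribution: more likely than not at entry week 36 over the stated range (58-74%), substantial at week 35 (37-50%), a minority at week 34 (16-30%) and small by week 32.

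One might infer a large loss for the trial as a whole. The protocol does not support that, because it gives no entry distribution: the result is 2 to 4 of 66 with even entry across the window, and 7 to 11 only if entry is concentrated in weeks 28-36. The consequence is some loss of precision and a T1 that mixes pregnant and post-partum states. It is worth correcting because the remedy is cheap.

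**What to change.** Reconcile the entry window with the 4-week follow-up in one of two ways:

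1. Align the window and the follow-up so that T1 falls within pregnancy. Which limit to use is for the investigators; none is proposed here.
2. Keep the window and schedule T1 for late entrants at 4 weeks or at a late session before expected delivery, whichever comes first, under the same rule in both arms.

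In either case, record the date of delivery and whether it preceded T1. Keep all randomised women in the intention-to-treat analysis already promised under Statistical analysis. Examine post-partum T1 values in a sensitivity analysis; excluding them from the main comparison would be a post-randomisation exclusion at odds with that promise. Adjust the comparison for gestational week at baseline, which is needed for eligibility anyway.

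The cost of the first option is some late-gestation recruits: about 8% of the window for each two weeks removed, if entry is even (2/24). The second costs no recruits. It means a somewhat shorter exposure before T1 for a few women and, because the delivery date is not known in advance, perhaps one or two repeated forms. A woman who delivers earlier than expected may still lack a T1 in pregnancy, so the second option reduces the problem without removing it.
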